The TECH intervention (study group) included daily self-training facilitated by weekly group sessions. Participants received iPads to take home and were requested to play puzzle-game apps, which simultaneously provided practicing different cognitive components, 3-5 times a week X 30-60 minutes, for a total of 15-25 training sessions. Weekly one-hour sessions led by an occupational therapist (OT) took place in a small group setting (4-6 participants) over a five-week period. These sessions focused on teaching tablet operation, allowing participants to explore and practice new apps, and increasing their confidence and independence in using and activating the tablet.

Standard care (control group). Participants received standard occupational therapy care for MCI including either a) a single consultation in a group setting (4-6 participants) to encourage participants to engage in activities such as solving crossword puzzles or playing board or card games in their leisure time to stimulate cognitive function; or b) participation in a social group (six one-hour sessions of 4-6 participants) of playing puzzle board games, with no recommendation to perform self-training at home.

Procedure

Participants were approached by phone and were provided with information about the study. Those who were willing to participate were invited to the geriatric clinic for the assessment session. After signing an informed consent form, the MoCA, GDS, BADL,

and IADL questionnaires were administered to confirm eligibility. If the participants were found eligible, the remaining outcome measures were administered. Then participants were stratified according to low (19-22 points) or high (23-25 points) MoCA score and then randomly allocated to the TECH or control group using a 1:1 ratio. Allocation was concealed from the investigators and the enrolled participants. Participants were notified by phone about their allocation. The assessors, who were blind to group allocation, were OTs trained to assess the study. Participants who were invited to the post- and follow-up assessment sessions were asked not to discuss the intervention with the assessors.

Data analysis

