'IBM SPSS Statistics 25' software was used for descriptive statistics to characterize the sample and outcome measures for the three assessments. Since the outcome measures were not normally distributed, non-parametric tests were performed. Intention-to-treat analysis was conducted with the last observation carried forward method, which is an acceptable data imputation method.²⁶ The percentage change was calculated for MoCA, WebNeuro, and SF-12 measurements between pre and post and between pre and follow-up using these formulas[(post-pre)/pre*100%], [(follow-up-pre)/pre*100%]. The difference between groups for the percentage change was tested using the Mann Whitney Test. Since significance tests are highly dependent on the sample size, the effect size was also estimated by using the effect size formula for non-parametric tests: Cohen's $r=Z/\sqrt{N}$. The Z value was retrieved from the Mann Whitney test U output. Cohen's r effect size values were considered small (0.1), medium (0.3), and large (0.5).

In each group, we calculated the percentage of participants who achieved the Minimal Clinically Important Difference (MCID) improvement in global cognition. MCID is defined as the smallest change in scores perceived by the patient as beneficial, which could lead to a change in the patient's treatment. In this study, the MCID of the MoCA was considered an improvement of at least 1.22 points, as found in Stroke Rehabilitation (since MCID data for individuals with MCI, to the best of our knowledge, have not yet been established).

The sample size was calculated using 'G*Power 3.1.9.4' software, according to a small effect size, based on previous studies assessing the effectiveness of computerized cognitive training for older adults with MCI, with 80% power and a significance level of 0.05. A sample size of 68 participants was calculated. Taking into consideration a 20% drop-out rate, 80 participants were required.

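### 68 participants do not give 80% power for a small effect under the planned Mann-Whitney test; power is about 12–13%, and the detectable effect is about 0.70 SD

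*Combined protocol and SAP*

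**What the plan says.** All but one of the relevant statements are in the Data analysis section.

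- **Effect size.** The calculation in G*Power was made "according to a small effect size, based on previous studies assessing the effectiveness of computerized cognitive training". No value, metric, standard deviation, test family or correlation is given.
- **Error rates.** It was run "with 80% power and a significance level of 0.05". Sidedness is not stated.
- **Result.** "A sample size of 68 participants was calculated". The next sentence adds: "Taking into consideration a 20% drop-out rate, 80 participants were required".
- **Test.** "The difference between groups for the percentage change was tested using the Mann Whitney Test". No other between-group test is described.
- **Scale.** The same section defines r as Z divided by the square root of N, with benchmarks of 0.1 for small, 0.3 for medium and 0.5 for large.

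The Procedure section supplies the allocation: participants were "randomly allocated to the TECH or control group using a 1:1 ratio", so 68 means 34 per arm.

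**The concern.** Thirty-four per arm is a familiar size for detecting a fairly substantial two-group difference, not a small one. The label, the number and the planned test cannot all be right together, and the plan's own r scale is enough to show it.

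This is the trial's only power statement. If it is taken at face value, a null result on the MoCA looks like evidence against even a small benefit, when the trial would miss such a benefit about seven times in eight. The statement also suggests that the trial was designed to pick up small effects, which would colour how any significant result is read.

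**Working it through.** **Inputs.** From the plan: total N = 68 (34 per arm), or 80 with the dropout allowance; power 80%; alpha 0.05; Mann-Whitney test; small r = 0.1. Assumed, because the plan does not say: a two-sided test (one-sided also shown); small as d = 0.2 where d is used, with d measured in SDs of the analysed change; and normal data for the Mann-Whitney efficiency of 3/π = 0.955 relative to the t-test.

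**1. Can 68 be reproduced for a small two-group effect?** No.

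- On the r scale: N = (1.960 + 0.842)² / 0.1² = 7.849 / 0.01 = 785.
- With d = 0.2, normal approximation: n per arm = 2 × 7.849 / 0.04 = 392.4, so 393 per arm and 786 in total.
- With d = 0.2, exact t-test: 394 per arm, 788 in total. Mann-Whitney: 824 in total.
- One-sided, d = 0.2, t-test: 620 in total. Sidedness does not explain the gap.

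The ratio to the stated figure is 785 / 68 = 11.5 at the low end and 824 / 68 = 12.1 for the Mann-Whitney test (two-sided).

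**2. What power does the design have for a small effect?** On the plan's formula, expected Z = 0.1 × √68 = 0.82, and power = Φ(0.82 − 1.96) = 0.128.

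| Total N | t-test, d = 0.2 | Mann-Whitney, d = 0.2 | Mann-Whitney, d for 80% power |
|---|---|---|---|
| 64 | 12.4% | 12.0% | 0.73 |
| 68 | 12.8% | 12.5% | 0.71 |
| 80 | 14.3% | 13.9% | 0.65 |

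A simulation of the Mann-Whitney test at 34 per arm (20,000 runs, normal data, d = 0.2) gave 12.2%. One-sided power at N = 68 is about 20%. An effect of d = 0.35 still has only 28% power (two-sided, Mann-Whitney).

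The row for 64 is there because 80 × 0.8 = 64: a 20% loss from 80 leaves fewer than 68. Covering that loss would take 68 / 0.8 = 85. The last-observation-carried-forward analysis may keep all 80, but power for a small effect is then still about 14%.

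**3. What effect does 68 correspond to?** Solving the r formula backwards: r = 2.802 / √68 = 0.34. A t-test at d = 0.70 needs exactly 68; the Mann-Whitney test needs 70. With 80% power at N = 68, the detectable d is 0.69 (t-test) to 0.71 (Mann-Whitney). That is between the usual medium and large for d, and slightly above medium on the plan's r scale.

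**4. Where might 68 have come from?** A repeated-measures ANOVA interaction, with noncentrality λ = f² × N × m / (1 − ρ), where m is the number of assessments and ρ their correlation, can give totals near 68.

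- f = 0.175, m = 2, ρ = 0.5 gives 68. In change-score terms this is √(4 × 0.175² × 2 / 0.5) = 0.70 SD.
- f = 0.1, m = 3, ρ = 0.8 gives 66. With ρ = 0.5 the same calculation gives 164.

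To convert the second case to the planned test, note that the SD of a change score is √(2 × (1 − 0.8)) = 0.632 raw SDs.

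- *Benefit present at post-test and held.* The interaction SD is δ/2 × √(2/9) = 0.236δ, so f = 0.1 gives δ = 0.424 raw SD. In change terms, 0.424 / 0.632 = 0.67. Mann-Whitney power is about 76% at 68 and 82% at 80.
- *Steady gain over the three assessments.* The interaction SD is δ/2 × √(1/6) = 0.204δ, so δ = 0.490 at follow-up and 0.245 at post-test. In change terms, 0.245 / 0.632 = 0.39 pre to post, with about 34% power at 68, and 0.490 / 0.632 = 0.77 pre to follow-up.

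**The case against.** The strongest reply is that the plan never says what small means in the sizing step. The r benchmarks appear where observed results are interpreted, not where G*Power is described, and f = 0.1 is also conventionally called small. The trial has three assessments. With f = 0.1 and a correlation of 0.8, a repeated-measures interaction needs 66, and if the benefit appears by post-test and holds, the Mann-Whitney test then has about 76% power at 68 and 82% at 80. On that reading the fault is an undisclosed metric and a mismatch between sizing test and analysis test, not a slip in arithmetic.

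Part of this stands. The 12–13% is conditional on small meaning r = 0.1 or d = 0.2 in the analysed change, and the origin of 68 may be a mismatch. But the rescue needs a test and a correlation that the plan does not name, a high value for that correlation (0.5 would require 164), and a sustained benefit. It also succeeds only because the implied difference in change is 0.67 SD, which is not small for the test used.

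Taking small as d = 0.2 on the raw score instead gives Mann-Whitney power at 68 of 12.5% if the pre-post correlation is 0.5, 24% if 0.8 and 43% if 0.9. None of these approaches 80%.

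It is also fair that the plan reports effect sizes because significance depends on sample size, and that it nowhere says a null result excludes a small benefit. That softens the likely harm but does not make the power statement true.

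**Conclusion.** The concern holds. For the only between-group test the plan describes, 68 participants give about 12–13% power for a small effect, not 80%, and about 14% if all 80 are analysed. The number needed is about 785 to 824. The effect that 68 can detect with 80% power is d of about 0.70, or r of about 0.34.

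These figures assume a two-sided test, 1:1 allocation, small as r = 0.1 or d = 0.2 in the analysed change, and normal data for the Mann-Whitney efficiency. A one-sided test raises the power only to about 20%. Whether the cause is an arithmetic error or a calculation made for a different test cannot be settled from the document; either way, the sentence is wrong as written for the planned analysis.

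**What to change.** Rewrite the sample-size paragraph for the test actually used. Suggested text: *With 68 participants (34 per arm), a two-sided Mann-Whitney test at 0.05 has 80% power for a standardised between-group difference in change of about 0.70 (r about 0.34). Power for a small effect (r = 0.1 or d = 0.2) is about 13%.*

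Remove the claim that the trial was sized for a small effect. Because the calculation has already been made, the sponsor should also disclose what was entered in G*Power: test, effect-size value and metric, sidedness and any correlation. The revised text then should not pass as the original rationale. The dropout step should be reconciled at the same time, since 80 less 20% is 64. Finally, state that a non-significant result does not rule out a small benefit.

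The cost is wording only, with no added participants. The price is a detectable effect that looks less favourable than the present text implies.

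### The allowance for drop-out is miscalculated: keeping 68 participants at 20% drop-out needs 85, not 80, and 80 keeps 68 only at 15% or less.

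*Combined protocol and SAP*

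**What the plan says.** The last paragraph of Data analysis reports a G*Power calculation made "according to a small effect size" and "with 80% power and a significance level of 0.05". Its result is given as "A sample size of 68 participants was calculated", and the next sentence allows for losses: "Taking into consideration a 20% drop-out rate, 80 participants were required". No inflation formula and no other drop-out rate is given.

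Two other statements bear on the point. Under Procedure, participants were "randomly allocated to the TECH or control group using a 1:1 ratio", so 68 means 34 per arm and 80 means 40 per arm. Earlier under Data analysis, the handling of missing data is set out: "Intention-to-treat analysis was conducted with the last observation carried forward method".

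**The concern.** When a calculated sample size is raised to allow for drop-out, the larger number should return the calculated one once the stated fraction has been lost. Here it does not: 80 reduced by 20% is less than 68.

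What is at stake is the tolerance for loss that the plan claims. A reader who compares actual retention with the plan, particularly at the 6-month follow-up, would take 20% as the level up to which the calculated number is protected. On the plan's own figures that level is 15%. A margin exists, but it is smaller than stated.

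**Working it through.** **Inputs, all from the sample-size paragraph of Data analysis except the allocation ratio (Procedure)**

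- Number calculated before drop-out: 68, or 34 per arm at 1:1
- Drop-out rate: 20%
- Number stated as required: 80, or 40 per arm
- Power 80%, significance level 0.05, sidedness not stated

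**Can the stated 80 be reproduced?**

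| Route | Calculation | Result |
|---|---|---|
| Divide by the retained fraction | 68 / (1 − 0.20) | 85 |
| Same, by arm | 34 / 0.80 = 42.5, rounded up to 43; 2 × 43 | 86 |
| Multiply by one plus the rate (a common shortcut) | 68 × 1.20 | 81.6, rounded up to 82 |
| Same, by arm | 34 × 1.20 = 40.8, rounded up to 41; 2 × 41 | 82 |

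No route gives 80. The shortcut comes closest and may be where the figure came from, but reaching 80 means rounding a minimum downwards. The shortcut is also wrong for a 20% loss of those enrolled: 82 × 0.80 = 65.6, still below 68.

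**What margin does 80 contain?**

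- Margin added: 80 − 68 = 12
- As a share of 80: 12/80 = 15.0%
- As a share of 68: 12/68 = 17.6%
- Losses expected at 20% of 80: 80 × 0.20 = 16, against a margin of 12

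The margin is 20% on neither base.

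**What does 80 deliver?**

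- At 20% drop-out: 80 × 0.80 = 64, which is 68 − 64 = 4 short
- Break-even drop-out: 1 − 68/80 = 15%; check: 80 × 0.85 = 68

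**Conditional effect on power**

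Assume that 68 gives exactly 80% power and that the test statistic is approximately normal, with a shift that grows with the square root of n. No effect-size value is then needed. With √(64/68) = 0.9701:

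- Two-sided 0.05: (1.960 + 0.842) × 0.9701 − 1.960 = 0.758, power 77.6%
- One-sided 0.05: (1.645 + 0.842) × 0.9701 − 1.645 = 0.767 (from unrounded quantiles), power 77.9%

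A two-sided t-test set to give 80% power at 34 per arm (which implies a standardised difference of about 0.69, an assumption not found in the documents) gives 77.5% at 32 per arm. All three put the loss at roughly 2 to 2.5 percentage points for a comparison of participants with complete data.

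**The case against.** The strongest reply is that the shortfall may never reach the planned analysis. The MoCA is given before randomisation, so every randomised participant has a baseline value, and carrying the last observation forward keeps drop-outs in the Mann-Whitney comparison. If 80 were randomised, about 80 would be analysed, which is more than 68. The figure of 64 applies only to participants with complete data, an analysis the plan does not name, so the power figures above do not describe the planned test.

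This stands as a limit on the consequence. It does not repair the sentence: the plan itself adds participants to cover drop-out, so it treats drop-out as a loss to be made good, and the addition is too small for the rate it names. Nor does carrying forward guarantee that power is kept. Someone with only a baseline value enters with 0% change under the plan's own formula, which adds a count but no observed outcome.

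A second reply is that 80 is a loosely rounded planning figure and the gap is only five people. That is plausible as an explanation, and it is a good reason to rate the point low. But the text presents 80 as the number required at 20%, not as an approximation.

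Third, the documents do not report how many were enrolled or lost, so the point concerns the stated requirement and shows nothing about the actual sample. That is correct and is accepted here.

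**Conclusion.** The stated requirement of 80 is inconsistent with 68 at 20% drop-out. It is 5 too few (85 needed), or 6 too few if arms are to be exactly equal (86). Put the other way, it leaves 4 fewer with complete data than calculated (64 against 68). These results use only the plan's own figures and the usual reading of a drop-out rate as a fraction of those enrolled.

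The point is minor. A fall from 80% to about 78% power holds only for participants with complete data and only if 68 gives exactly 80% power. No power figure can be given for the analysis with values carried forward. The 68 is taken as given: the size of the small effect, the test and the sidedness behind it are not stated, so it cannot be verified, and whether it is justified is a separate question that adds no weight here.

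**What to change.** Keep the existing planning sentence on record and add a dated correction beside it, for example:

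> Correction: enrolling 80 provides at least 68 participants with complete data if drop-out is 15% or less, and 64 at 20% drop-out; retaining 68 at 20% drop-out would have needed 85 (86 with equal arms).

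The 20% should not simply be replaced by 15%, because that would rewrite the planning assumption after the event.

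This assumes that enrolment is closed, which is inferred from the past tense of the methods and the March 2020 date; the documents do not say so outright. The cost is one added sentence, with no change to enrolment, endpoint, test or analysis set.
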